7.4.2 Analysis of Secondary Endpoints

The analysis of secondary efficacy endpoints will be based on the FAS.

For each of the secondary vasomotor symptom and patient-reported outcome endpoints, an MMRM model as described in Section 7.4.1.2 will be used. The treatment difference will be estimated at all study weeks (week replaced by visit for patient-reported outcome endpoints).

For each of the secondary responder endpoints, logistic regression will be used for the analysis for each week and endpoint. The analyses will include the treatment group and smoking status (current vs. former/never) as factors and baseline measurement (mean frequency of vasomotor symptoms) as a covariate. The missing value will be imputed as a non-responder.

[figure not shown]
For these responder endpoints, the number of subjects who achieve the reduction will be summarized by study week with descriptive statistics for each treatment arm. For 50% and 90% reduction responders, Kaplan-Meier estimate will be used to estimate the time to response and the time to sustained response. Smooth average (SA) will be used for the time to response. SA value for day X-1, day X and Day X+1 would be assigned to day X. The time to response will be the first day with at least 50% (or 90%) response for both original numbers and SA number. The time to sustained response will be the first day with at least 50% (or 90%) response for both original numbers and SA number, and SA response from that day till the end of the treatment at least 50% (or 90%) response on each day. For the non-responders, it will be censored at the end of treatment.

Diary interaction compliance will be summarized with descriptive statistics and presented by treatment group.

Plasma concentrations of hormones and bone turnover markers will be summarized with descriptive statistics for each treatment group at each visit. Additionally, a within-subject change will be calculated as the post-baseline measurement minus the baseline measurement and summarized in the same way. Pharmacodynamic data and efficacy data may be evaluated by a population PD or population PK/PD approach. All details of population analyses will be described in a separate analysis plan and a separate report will be written. When deemed necessary, data from this study may be combined with data from other studies.

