4 SAMPLE SIZE

A total of 352 subjects are planned to be randomized, 44 subjects in each treatment arm.

In the Phase 2a study, the observed least-squares mean difference between ESN364 90 mg BID (highest dose of this Phase 2b study) and placebo in change from baseline to Week 12 in mean daily frequency of moderate to severe vasomotor symptoms was -5.0 (95% CI: - 6.8, -3.3) with similar results at Week 4. For any given pairwise comparison for a 2-sample t-test at a 2-sided 5% alpha, 40 subjects provides the following power to detect the following effect sizes assuming an SD of 5:

Assumed treatment difference in mean daily frequency	Power for pairwise test
3.3	83%
3.5	87%
4	94%
4.5	97%
5	>99%

For change from baseline to Week 12 in mean severity of moderate to severe vasomotor symptoms, the observed mean treatment difference in the Phase 2a study was -1.12 (95% CI: -1.5, -0.74) with similar results at Week 4. For any given pairwise comparison for a 2-sample t-test at a 2-sided 5% alpha, 40 subjects provides the following power to detect the following effect sizes assuming an SD of 1:

Assumed treatment difference in mean severity	Power for pairwise test
0.64	80%
0.75	91%
1	>99%

Note that the combined power for testing all 4 co-primary endpoints will be lower than the power for each considered individually. Assuming approximately 10% of subjects discontinue prematurely, the number of 40 subjects is increased to 44 subjects per arm.

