- Mean percent reduction of 50%, 70%, 90%, and 100% of mild, moderate, and severe vasomotor symptoms from baseline to each study week;
- Mean percent reduction of 50%, 70%, 90%, and 100% of moderate and severe vasomotor symptoms from baseline to each study week;
- Absolute reduction of 2, 3, 4, and 5 in mean number of mild, moderate, and severe vasomotor symptoms per 24h from baseline to each study week; and
- Absolute reduction of 2, 3, 4, and 5 in mean number of moderate and severe vasomotor symptoms per 24h from baseline to each study week.

6.1.2.3 Patient-Reported Outcome Endpoints:

- Change in Hot Flash Related Daily Interference Scale (HFRDIS) from baseline to Weeks 4, 8, 12, and 15;
- Change in Leeds Sleep Evaluation Questionnaire (LSEQ) from baseline to Weeks 4, 8, 12, and 15;
- Change in Greene Climacteric Scale (GCS) from baseline to Weeks 4, 8, 12, and 15; and
- Change in Menopause-Specific Quality of Life (MENQoL) from baseline to Weeks 4, 8, 12, and 15.

HFRDIS: The HFRDIS is a 10-item scale that measures a woman's perceptions of the degree to which vasomotor symptoms interfere with 9 daily life activities (work, social activities, leisure, sleep, mood, concentration, relations with others, sexuality, and enjoying life); the 10th item measures interference with overall quality of life.⁵ This scale was modeled after items on the Brief Pain Inventory⁶ and Brief Fatigue Inventory,⁷ which assess the extent to which pain or fatigue interfere with daily life. Subjects will be asked to rate the extent to which vasomotor symptoms have interfered with each item during the previous 2-week time interval using a 0 (do not interfere) to 10 (completely interfere) scale. Recent structural equation modeling suggests the HFRDIS is a unidimensional scale best represented by an overall mean score calculated as the sum of items/10.⁸ If any of the 10 items have missing values, the overall mean score will not be calculated.

LSEQ: The LSEQ is a 10-item self-rated questionnaire that assesses a subject's aspects of sleep and early morning behavior. The questions are grouped into 4 chronological domains: ease of getting to sleep (items 1 to 3), perceived quality of sleep (items 4 to 5), ease of

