7 STATISTICAL METHODOLOGY

7.1 General Considerations

For continuous variables, descriptive statistics will include the number of subjects (n), mean, standard deviation, minimum, median, maximum, 10%, 90%, and lower and upper quartiles. Frequencies and percentages will be displayed for categorical data. Percentages by categories will be based on the number of subjects with no missing data, i.e. will add up to 100%.

Summaries based on FAS and PPS (e.g. disposition, baseline and efficacy data) will be presented by planned treatment group, unless specifically stated otherwise. Safety analysis and other summaries based on SAF will be presented by actual treatment received.

All statistical comparisons will be conducted using two sided tests at the $\alpha=0.05$ significance level unless specifically stated otherwise. All null hypotheses will be of no treatment difference, all alternative hypotheses will be two-sided, unless specifically stated otherwise.

All data processing, summarization, and analyses will be performed using SAS[®] Version 9.3 or higher on Windows[®]. Specifications for tables, figures, and data listing formats can be found in the TLF specifications.

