7.10 Handling of Missing Data, Outliers, Visit Windows, and Other Information

7.10.1 Missing Data

If there are no diary entries for a particular calendar day, and the patient reported receiving at least one morning dose of study medication or at least one evening dose of study medication on that day, the frequency of vasomotor symptoms will be imputed to 0; otherwise, the frequency of vasomotor symptoms will be considered missing.

If no vasomotor symptoms were recorded for the day, and the patient reported receiving at least one morning dose of study medication and at least one evening dose of study medication on that day, the severity will be 0.

Missing primary endpoints will be handled by multiple imputation for continuous variables, and non-responder imputation for binary variables.

For study drug compliance, the capsules returned will be imputed to 0 at the visit if no bottle was returned for a visit.

Multiple Imputation Method:

Multiple imputation will be used to impute missing data and will be implemented using SAS® PROC MI. Missing data may be the result of missing Week 4/Week 12 frequency/severity of vasomotor symptoms measurements or the result of patients discontinuing treatment prior to Week 4/Week 12. Missing at random will be assumed.

The imputation model will include the subject demographics (age [$<$ median, \geq median], race [white, non-white], baseline weight [$<$ median, \geq median], and smoking status), and baseline and post-baseline frequency/severity of vasomotor symptoms. Missing data will be imputed 100 times to generate 100 complete data sets. The seed will be 98765. The fully conditional specification method will be used. The 100 complete data sets will then be analyzed using the same analysis method as the one used to analyze the primary endpoint. See Section [7.4.1.1](#). The results from the 100 fitted models will be combined using SAS® PROC MIANALYZE.

If the model fails to converge, exclusion of subject demographics will be considered.

Safety Data Imputation:

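### The responder logistic regressions have no rule for empty cells: if placebo has no responders, the odds ratios against placebo are not finite, and the p-value depends on a test the SAP does not name

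*SAP*

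**What the plan says.** SAP 6.1.2.2 defines responders at four relative thresholds, for example "Mean percent reduction of 50%, 70%, 90%, and 100% of moderate and severe vasomotor symptoms from baseline to each study week", and at absolute reductions of 2 to 5 per 24 hours. Each is defined for two symptom sets (all severities, and moderate plus severe) and for each study week. Responder rates are a stated secondary objective in both documents.

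SAP 7.4.2 gives the analysis: "For each of the secondary responder endpoints, logistic regression will be used for the analysis for each week and endpoint". On the model terms it says: "The analyses will include the treatment group and smoking status (current vs. former/never) as factors", with baseline mean frequency as covariate. On missing data: "The missing value will be imputed as a non-responder". Responder counts are also summarised by arm and week.

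SAP 7.1 sets the general frame: "All statistical comparisons will be conducted using two sided tests", at the 0.05 level, and "All data processing, summarization, and analyses will be performed using SAS". Neither section says whether the logistic p-values are Wald, score or likelihood-ratio, or what happens if an arm has no responders. The SAP does plan for model failure elsewhere: 7.4.1.1 allows pooled center to be dropped from the ANCOVA, and 7.10.1 allows demographics to be dropped from the imputation model.

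**The concern.** In a logistic model with treatment as a factor, an arm with no responders has a fitted log-odds that runs to minus infinity. If that arm is placebo, every comparison with a dose that has responders has an infinite odds ratio. All such contrasts in that fit are lost together, because they share the comparator. The Wald standard error grows faster than the estimate, so a Wald p-value drifts towards 1 however large the observed difference.

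Empty cells are most foreseeable at the highest thresholds. A 100% reduction needs a weekly mean of zero, in women who qualified with at least 50 moderate to severe symptoms in a week (50/7 = 7.1 per day), and Week 1 includes the first day of dosing. At stake are the odds ratios, intervals and p-values for part of a secondary objective, and the freedom to pick a test after the zero cell has been seen.

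**Working it through.** **Inputs from the documents.** SAP section 4: "A total of 352 subjects are planned to be randomized, 44 subjects in each treatment arm", with 40 per arm after the allowance for discontinuation (40 × 1.1 = 44; 44 × 8 = 352). The documents give no power figure, expected placebo rate or other number for the responder analysis, so there is no planned figure to reproduce. The placebo rates below are assumptions.

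**Number of exposed fits.** 90% and 100% thresholds × 2 symptom sets × 12 on-treatment weeks = 2 × 2 × 12 = 48 fits, or 48 × 7 = 336 contrasts with placebo. This is the most that could be exposed, not the number expected to fail.

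**Chance of an empty placebo cell.** P(no responders) = (1 − p)^n in a given week:

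| True placebo rate p (assumed) | n = 40 | n = 44 |
|---|---|---|
| 1% | 67% | 64% |
| 2% | 45% | 41% |
| 5% | 13% | 10% |
| 10% | 1.5% | 1.0% |
| 20% | <0.1% | <0.1% |

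At a constant 2% rate and n = 40, the expected number of affected weeks per endpoint is 12 × 0.446, about 5 of 12. At 10% it is 12 × 0.015, about 0.2.

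**What maximum likelihood does at 10/44 versus 0/44 (two-group model).**
- Wald: estimate 22.3, SE 11,979 where the software stopped; z = 22.3/11,979 = 0.0019, p = 0.9985. The estimate and SE depend only on when iteration stops.
- Likelihood ratio: log-likelihood under no difference = 10 ln(10/88) + 78 ln(78/88) = −31.16. With separate arms it is 10 ln(10/44) + 34 ln(34/44) = −23.58. Twice the difference is 15.15 on 1 df, p = 0.0001.
- Fisher's exact test: p = 0.001.

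**The SAP's eight-arm model.** With 40 per arm, placebo 0/40, active rates of 10% to 40%, and simulated smoking and baseline frequency, Wald p-values for all seven contrasts were 0.58 to 0.66 after 8 iterations and about 1.00 after 20. Likelihood-ratio tests on the same fits gave p = 0.0006 at 20% active, 1.6 × 10⁻⁵ at 30% and 3.8 × 10⁻⁷ at 40%. The simulated covariates do not affect the separation result. Changing one placebo subject to a responder made all seven log odds ratios finite (1.45 to 3.24).

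**Smaller differences, where the unnamed test decides the result.** At 4/40 versus 0/40 (two-group model): likelihood ratio p = 0.016, Firth penalised likelihood ratio p = 0.049, Fisher p = 0.12, Wald about 1.

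**The remedy on the same kind of table.** In a two-group model the Firth estimate equals adding 0.5 to each cell. At 10/44 versus 0/44 the odds ratio is (10.5 × 44.5)/(34.5 × 0.5) = 27.1, with profile penalised-likelihood 95% CI 3.3 to 3,528 and penalised likelihood-ratio p = 0.0004. At 6/40 versus 0/40 the odds ratio is 15.3, with penalised likelihood-ratio p = 0.010 but Firth-with-Wald p = 0.070. The test has to be named along with the estimator.

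**The case against.** A reader might infer that the trial's clearest responder effects would be reported as non-significant. The documents do not support that, for four reasons:

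- **The test.** Values near 1 arise only with Wald tests, and the SAP names no test. Likelihood-ratio or exact tests on clearly different arms stay significant.
- **The trigger.** It depends on a placebo rate the documents do not give. Protocol 5.2 expects a placebo effect. SAP 7.10.1 adds possible responders: on a dosed day without a diary entry, "the frequency of vasomotor symptoms will be imputed to 0". A weekly value also needs only 3 days with any information. Non-responder imputation pushes the other way. At 10% or more the problem is rare.
- **The effect size.** A zero placebo cell is not always a clear effect, as 4/40 versus 0/40 shows. If an active arm is also empty, that odds ratio is not infinite but indeterminate.
- **Other reporting.** Counts by arm and week would show the difference. Percent reduction is also analysed as a continuous endpoint, 50% and 90% responders get Kaplan-Meier time to response, and SAP section 1 lets departures be justified in the study report.

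All of this stands, and it limits the reach of the point. It does not remove it. Even with a likelihood-ratio test, the odds ratio and its upper limit are not finite when placebo has no responders. An unnamed test leaves the choice to be made after the data are seen, and a justification in the study report would also come after unblinding.

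**Conclusion.** The point holds as a gap in a secondary analysis. SAP 7.4.2 applies logistic regression to every threshold and week with no provision for empty cells. If placebo has no responders, maximum likelihood gives no finite odds ratio for any dose with responders, and none at all for a dose without. That follows from the model and needs no assumption.

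How often it happens does need one. It is likely in a given week (41% to 64% with 44 per arm) only at a true placebo rate of about 1% to 2%, which is plausible for 100% reduction in early weeks and less certain for 90%. It falls to 10% at a rate of 5% and to 1% at 10%. Whether a clear difference would also lose its p-value depends on a Wald test being used, which the SAP neither states nor rules out.

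The responder endpoints lie outside the step-down procedure, so no co-primary conclusion changes. This is a minor improvement, worth making because it is cheap.

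**What to change.** Add to SAP 7.4.2, before unblinding, that responder endpoints are analysed by Firth penalised-likelihood logistic regression with the covariates already listed, profile penalised-likelihood confidence intervals, and penalised likelihood-ratio p-values rather than Wald p-values. This can apply to all responder endpoints, or only under a pre-stated rule: whenever any arm has zero responders or all responders at that threshold and week. If the rule is used, name the test for the ordinary fits as well.

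The cost is a sentence or two in the SAP and a small change to the program, with no new data and no design change. Applied throughout, the method shrinks odds ratios slightly in well-populated cells such as the 50% threshold. Applied by rule, it avoids that but mixes two estimators across weeks, so the tables should mark which was used. Intervals from empty-cell fits will be wide (3.3 to 3,528 in the example above).

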7.4.3 Analysis of Exploratory Endpoints

CCI

Pharmacokinetics may be evaluated by a population PK approach. All details of population analyses will be described in a separate analysis plan and a separate report will be written. When deemed necessary, data from this study may be combined with data from other studies.

Weight and waist circumference will be summarized with descriptive statistics for each treatment group at Baseline and at Weeks 4, 8, 12, and 15. Additionally, a within-subject change will be calculated as the post-baseline measurement minus the baseline measurement and summarized in the same way.

The mean frequency of moderate to severe 12h day time and 12h night time vasomotor symptoms as well as change from baseline will be summarized by study week and for the Last on Treatment Week. See Section 7.10.6 for study week and endpoint derivations. Additionally, the analysis of exploratory efficacy endpoints will be based on the FAS. An analysis of covariance model as described in Section 7.4.1.1 will be used.

7.5 Analysis of Safety

All analyses of safety will be presented by treatment group for SAF, unless specified otherwise. For analyses by visit, the visit windows from Section 7.10.6 will be applied. Except for adverse events and follow-up visit data, only data up to one day after the last dose date will be considered for the analyses.

7.5.1 Adverse Events

Summaries and listings of SAEs and Serious TEAEs include SAEs upgraded by the sponsor based on review of the Sponsor's list of Always Serious terms if any upgrade was done.

The coding dictionary for this study will be MedDRA. It will be used to summarize AEs by SOC and PT.

An overview table will include the following details:

- Number of TEAEs,
- Number and percentage of subjects with TEAEs,
- Number of drug related TEAEs,
- Number and percentage of subjects with causally drug related TEAEs,
- Number of serious TEAEs,
- Number and percentage of subjects with serious TEAEs,
- Number of serious drug related TEAEs,
- Number and percentage of subjects with serious drug related TEAEs,
- Number of TEAEs leading to permanent discontinuation of study drug,
- Number and percentage of subjects with TEAEs leading to permanent discontinuation of study drug,
- Number and percentage of subjects with TEAEs leading to study drug interruption, and
- Number of deaths.

The number and percentage of subjects with TEAEs, as classified by SOC and PT will be summarized for each treatment group. Summaries will be provided for:

- TEAEs,
- drug related TEAEs,
- serious TEAEs,
- drug related serious TEAEs,

- TEAEs leading to permanent discontinuation of study drug,
- drug related TEAEs leading to permanent discontinuation of study drug,
- TEAEs excluding serious adverse events that equal to or exceed a threshold of 5% in any treatment group, and
- common TEAEs that equal to or exceed a threshold of 5% in any treatment group.

The number and percentage of subjects with TEAEs, as classified by PT only, will be summarized for each treatment group.

The number of TEAEs and the number and percentage of subjects with TEAEs, as classified by SOC and PT will also be summarized by severity and by relationship to study drug. In the subject count, if a subject has multiple TEAEs with the same SOC or PT, but with differing severity or relationship, then the subject will be counted only once with the worst severity and highest degree of relationship, however, if any of the severity or relationship values are missing then the subject will be counted only once with missing severity or relationship. In the adverse event count, the adverse events will be presented in each category they were classified to. Drug related TEAEs will be presented in a similar way by severity only.

Adverse events of special interest oral/ facial paresthesia, uterine bleeding and elevation in ALT and/or AST >3 x ULN. A summary table and detailed listing of adverse events of special interest will be provided. A burden of toxicity graph will be generated for the adverse events of special interest.

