6.2 Safety Variables

Safety variables will include the following:

- Incidence and severity of treatment-emergent adverse events (TEAEs);
- Endometrial health assessment (transvaginal ultrasound ± endometrial biopsy);
- Vital signs (sitting systolic and diastolic blood pressure and pulse rate);
- Laboratory tests (hematology, biochemistry, urinalysis, and coagulation);
- 12-lead electrocardiogram (ECG) parameters;
- Plasma bone density marker concentrations;

- Physical examinations; and
- Columbia Suicide Severity Rating Scale (C-SSRS).

A TEAE is defined as an adverse event observed after starting administration of study drug through 7 days after the last dose of study drug. If the adverse event occurs on the day of the first dose and the onset time is on or after the time of the first dose of study drug or the onset time is missing, then the adverse event will be considered treatment emergent. If the adverse event occurs on the day of first dose and the onset time is before the time of the first dose of study drug, then the adverse event will not be considered treatment emergent. If a subject experiences an event both during the pre-investigational period that continues into the investigational period, the event will be considered as TEAE only if it has worsened in severity (i.e. it is reported with a new start date).

A drug-related TEAE is defined as any TEAE related to study treatment as assessed by the investigator or with missing assessment of the causal relationship.

Other safety endpoints will be considered treatment emergent if observed after starting administration of study drug through 1 day after the last dose of study drug.

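### In the adverse-event subject counts, one missing grade moves a subject with a known severe or related event into the 'missing' row

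*SAP*

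**What the plan says.** SAP 7.5.1 asks for TEAEs by SOC and PT, broken down by severity and by relationship, with event counts and subject counts. The subject-count rule has three parts.

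- It applies "if a subject has multiple TEAEs with the same SOC or PT, but with differing severity or relationship".
- By default, "the subject will be counted only once with the worst severity and highest degree of relationship".
- The default is then overridden: "if any of the severity or relationship values are missing then the subject will be counted only once with missing severity or relationship".

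Two further sentences set the scope. For event counts, "In the adverse event count, the adverse events will be presented in each category they were classified to". The subject rule is also carried over to a further table: "Drug related TEAEs will be presented in a similar way by severity only".

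SAP 6.2 has its own convention for causality: "A drug-related TEAE is defined as any TEAE related to study treatment as assessed by the investigator or with missing assessment of the causal relationship". It names severity as a safety variable but has no rule for an ungraded event. Protocol 9.1.3 collects severity as mild, moderate or severe, and relationship as yes or no, so 'missing' is not a category that an investigator can choose.

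**The concern.** A worst-case subject count is meant to answer how many women had at least one severe (or related) event under a term. Once one such event is documented, the answer for that woman is yes, whatever is unknown about her other events. The override replaces this known answer with an unknown one.

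The direction is one-sided: against a count at the worst known value, the severe and related rows can stay the same or fall, but never rise. Women with more events under a term have more chances of an ungraded one, so an arm with more events would be more exposed. This matters somewhat in a dose-ranging study that lists safety and tolerability among its secondary objectives.

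For causality there is a second issue. The drug-related tables in 7.5.1 rest on the 6.2 definition, while the by-relationship table in the same section puts the same woman in a 'missing' row. The two can then show different numbers for the same SOC or PT.

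**Working it through.** The documents give no figure for this rule, so there is nothing to reproduce. The check is logical, with a sensitivity range added. I read the override as acting on each variable separately: a missing severity affects the severity table, and a missing relationship affects the relationship table.

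**1. Example.** A woman has a severe event of PT A and an ungraded event of PT B in the same SOC. Under 7.5.1 the PT A row shows her as severe and the PT B row as missing, which is correct. The SOC row shows her as missing, although she is known to have had a severe event in that class. If both events share one PT, the PT row is affected too.

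**2. Severity, by enumeration.** Each event is mild, moderate, severe or missing.

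- Two events: 4² − 3² = 16 − 9 = 7 patterns contain a severe event. Of these, 16 − 9 − 9 + 4 = 2 also contain a missing grade and are shown as missing.
- Three events: 4³ − 3³ = 64 − 27 = 37 patterns contain a severe event. Of these, 64 − 27 − 27 + 8 = 18 are shown as missing.

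If 'missing' were kept for subjects with no graded event, both counts would be 0. These are counts of patterns, not probabilities. The subject counts cannot be repaired afterwards, because a woman in the 'missing' row may hold a mild, moderate or severe event.

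**3. Relationship, by enumeration.** Each event is no, yes or missing. For one to five events there are 3 + 9 + 27 + 81 + 243 = 363 patterns.

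- SAP 6.2 classes the woman as drug related if any event is yes or missing.
- SAP 7.5.1 shows her as missing if any event is missing, otherwise as related if any event is yes.
- Related plus missing under 7.5.1 equals drug related under 6.2 in all 363 patterns (0 mismatches).
- In 244 of the 363, a woman with a known related event is shown as missing, so the related row alone falls short of the 6.2 count.

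**4. How often it could happen.** Let m be the share of events whose severity is still missing after queries, and k the number of her events under the term, one of them known to be severe. If values are missing independently, the chance that she is moved to 'missing' is 1 − (1 − m)^(k−1). The documents give no m; the values below are assumptions.

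| m | k = 2 | k = 3 | k = 5 |
|---|---|---|---|
| 0.5% | 0.5% | 1.0% | 2.0% |
| 1% | 1.0% | 2.0% | 3.9% |
| 2% | 2.0% | 4.0% | 7.8% |
| 5% | 5.0% | 9.8% | 18.5% |

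For example, m = 5% and k = 5 gives 1 − 0.95⁴ = 1 − 0.8145 = 18.5%.

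**5. Weight of one subject.** With 44 planned per arm, 1/44 = 2.3 percentage points.

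**The case against.** The strongest reply is that little is lost and the trigger will be rare.

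- *The severe events stay visible.* A reader might infer that the rule hides the worst events. The documents do not support that. The event count in the same summary keeps each event in its own category, and nothing makes the tables of serious TEAEs, discontinuations, deaths or events of special interest depend on this rule. This stands, and it confines the problem to subject counts in the by-severity and by-relationship breakdowns, including drug-related TEAEs by severity.
- *Section 6.2 is not contradicted on severity.* A reader might take the whole rule as contrary to 6.2. That section covers only "or with missing assessment of the causal relationship" and is silent on ungraded severity. The severity half is a weakness inside 7.5.1.
- *The causality difference is one of labelling.* This is correct as far as it goes, since adding two rows restores the 6.2 count. But the reader must know to add them, and the row labelled related is still too low on the plan's own definition.
- *Missing grades should be few.* Protocol 9.1.3 requires both assessments for every event, Protocol 11.1.1 treats an eCRF as complete only once missing data are accounted for, and Protocol 11.1.5 sends missing data back to the site. This limits the size but does not justify the rule.
- *Showing missing as missing fits SAP 7.10.1,* which as a general principle does not impute other variables. But counting a documented severe event as severe imputes nothing.

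**Conclusion.** The point holds for the subject counts. The override gives a wrong answer for any woman who has both a known severe (or related) event and an event with a missing value under the same term, and the error always lowers the severe or related row. On relationship it is inconsistent with 6.2 in a way that can be reconciled; on severity the subject counts cannot be reconciled.

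The size is small and cannot be fixed from the documents. It needs a value that stays missing after queries in a woman with another event under that SOC or PT, and the chances tabulated above rest on assumed missing rates and independence. The 2.3 percentage points should not be read as an expected bias: it is what any single subject weighs in any table of an arm of 44. If no values are missing at lock, the rule has no effect. No efficacy conclusion depends on it. This is a minor correction worth making because it is cheap.

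**What to change.** Replace the override in SAP 7.5.1 with three statements:

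- A subject is counted at her worst known severity under the SOC or PT, so a known severe event always counts as severe. 'Missing' is used only when none of her events under that term is graded.
- A missing relationship is counted as related, as in 6.2, so that the related row and the drug-related tables agree.
- A footnote gives the number of subjects with one or more ungraded events, by arm.

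The footnote is needed because the change has a downside: a woman with one mild and one ungraded event would be shown as mild, although the ungraded event might have been worse. Her incomplete data would otherwise disappear from view.

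The cost is one amended sentence, a footnote and a small programming change, with no new data. It is best made before hard lock and unblinding; SAP 1 requires any change from the planned analyses to be justified in the CSR.
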